## **Background/Significance:**

Femoroacetabular impingement (FAI) is a condition first described by Ganz et al. in 2003 characterized by bony abnormalities of the femoral head and acetabulum^1. FAI can be divided into two groups based on this anatomic deformity—those that involve the femoral head-neck junction (cam impingement) or acetabulum (pincer impingement). Because of these morphological alterations, contact can occur between the femur and acetabulum at normal ranges of motion. Repetitive contact because the femoral head and acetabulum can result in damage to the labrum and adjacent articular cartilage. FAI can give rise to pain and is widely regarded as the initiating factor for the onset of hip osteoarthritis. At this point changing the bony abnormality and its effect of the natural history of FAI is unknown. As a result the initial treatment of FAI is non-surgical and includes activity modification, physical therapy, and anti-inflammatory drugs. Corticosteroid injections are commonly used in orthopedics to treat the pain and inflammation of joint and soft tissue conditions. Despite the current use of corticosteroid for the treatment of musculoskeletal conditions and the increased role of platelet rich plasma (PRP), there are no available studies evaluating their role in the treatment of FAI.

More recent treatment efforts have focused on cellular based therapies such as platelet rich plasma (PRP) for the treatment of joint and soft tissue conditions. PRP is defined as a volume of plasma fraction from autologous blood with platelet concentrations above baseline. Platelets contain many bioactive proteins and growth factors that could potentially accelerate healing and stimulate anti-inflammatory properties. Recent studies show promising clinical results with intra-articular PRP injections for symptomatic knee osteoarthritis. Animal studies have also shown positive effects in stimulating cartilage matrix metabolism in osteoarthritis affected animal joints.

#### **Purpose:**

The purpose of this double-blinded study is to compare the clinical response of intra-articular platelet rich plasma (PRP) versus corticosteroid injection in patients affected by femoroacetabular impingement (FAI).

## **Specific Aims:**

**Specific Aim 1:** To assess the effect of PRP treatment of FAI symptoms compared to standard corticosteroid treatment.

Hypothesis 1: We hypothesize that compared to corticosteroids, patients with FAI that are treated with PRP will have (i) lower pain scores (ii) improved Hip Disability and Osteoarthritis Outcome Score (HOOS), Patient Reported Outcome Measurement Information System (PROMIS) Global Health Scale scores and (iii) increased hip stability scores as measured by BioDex stability station functional testing.

**Specific Aim 2:** To determine if PRP treatment of FAI reduces (i) radiographic and (ii) biochemical markers of joint inflammation and cartilage degradation.

Hypothesis 2: We hypothesize that compared to corticosteroids, patients with FAI that are treated with PRP will have (i) a diminished change in Kellgren-Lawrence radiographic scores and (ii) reduced levels of circulating biomarkers C-reactive protein, cartilage oligomeric matrix protein and type II collagen propeptide levels in circulation.

# **Primary Outcome:**

• Pain as measured by Visual Analog Scale (VAS)

## **Secondary Outcome(s):**

- Patient reported function and symptoms
- Evaluate performance of serum biomarkers
- Change in Kellgren-Lawrence classification scores calculated from anterior-posterior (AP) pelvis radiographs between pre-treatment and 1 year post-treatment

#### Plan for measurement of these outcomes:

- The Primary outcome measures will be:
  - o Change in 7 point pain Visual Analogue Scale (VAS)
- Secondary outcome measures include:
  - Hip Disability and Osteoarthritis Outcome Score (HOOS)
    - Western Ontario and McMaster Universities Arthritis Index (WOMAC), calculated as a subscore of the HOOS
  - Patient Reported Outcome Measurement Information System (PROMIS) Global Health Scale
  - o Serum Biomarker analysis: IFN-g, IL-6, MCP-1, MIP-1b, IL-1b, TNF-alpha, high-sensitivity CRP, COMP
  - Change in Kellgren-Lawrence classification scores calculated from AP pelvis radiographs between pre-treatment and 1 year post-treatment

## **Methods:**

#### **Inclusion Criteria:**

- Patients with symptomatic FAI with duration of symptoms for at least 6 weeks
- Clinical and radiographic evidence of FAI defined as the presence of a cam, pincer or combined lesion apparent from radiographs
- Mild to moderate osteoarthritis (Kellgren-Lawrence grade  $\leq 2$ )
- Patients able to provide consent to study participation
- VAS pain level of  $\geq 5$

#### **Exclusion Criteria:**

- High grade osteoarthritis (Kellgren-Lawrence  $\geq 3$ )
- Minimum joint space < 2 mm as measured on AP radiograph
- Hip dysplasia (center edge angle < 20° on AP radiograph)
- Patients with clinically significant cardiovascular, renal, hepatic, endocrine disease, cancer or diabetes
- Patients with ongoing infection including Tuberculosis, HIV and Hepatitis
- Patient with history of osteomyelitis/septic arthritis or active infections near the joint
- Anticoagulation therapy
- Patients who are pregnant or breast feeding
- Patients with systemic, rheumatic or inflammatory disease of the knee or chondrocalcinosis, hemochromatosis, inflammatory arthritis, arthropathy of the knee associated with juxtaarticular Paget's disease of the femur or tibia, hemophilic arthropathy, infectious arthritis, Charcot's knee joint, villonodular synovitis, and synovial chondromatosis
- Patients taking immunosuppressant medication
- Patients with a recent history of abnormal hematology or serum chemistry lab results which is interpreted by investigation team as clinically significant
- Patients receiving any injectable treatment to affected hip within 2 months of study enrollment
- BMI greater than 35 or less than 20
- Known hypersensitivity to kenalog, or lidocaine or any of the components

Minimum Age: 18 Maximum Age: 45

Number of Subjects to be included in study: N = 40 (n = 20 per arm)

Proposed Study Start Date: 7/1/16 Proposed Study End Date: 6/30/18

#### **Summary of Human Subject Involvement:**

Patients with symptomatic femoroacetabular impingement (FAI) identified from our MedSport clinic will be potential candidates for this study. The diagnosis of FAI is based on the guidelines described by Ganz. Exclusion/inclusion criteria are described above. Baseline data will include radiographs, serum biomarkers, pregnancy test, and clinical data regarding hip pain. Patients

will be randomized to one of 2 treatment arms: A) ultrasound guided hip intra-articular corticosteroid injection; or B) ultrasound guided hip intra-articular platelet rich plasma injection.

Follow-up will be obtained at 6 weeks, 3 months, 6 months and 12 months. At each follow-up visit, the following will be collected:

- 1. 7-point visual analog pain scale;
- 2. The WOMAC, the HOOS, and the PROMIS Global Health scale;
- 3. Radiographs (initial encounter and 12 months only);
- 4. Serum biomarkers (IFN-g, IL-6, MCP-1, MIP-1b, IL-1b, TNF-alpha, highly sensitive CRP, COMP) at all time points.

#### Screening:

X days prior to randomization, potential subjects will have the following tests done as part of screening for eligibility:

- A history and physical examination, including height and weight and BMI calculation;
- Clinical assessment of hip pain; including history, physical exam and subjective patient reporting.
- Radiographs; including standing AP pelvis, Dunn lateral views and false profile view
- Blood will be drawn for serum biomarkers;
- Serum or urine pregnancy test for females of child bearing potential

#### Patient Selection:

[name] and [name] see patients with hip pain as part of their routine clinical practice. They will do all the screening of potential patients. Once a patient has been enrolled in the study, he/she will be rescheduled and that subsequent visit will serve as their initial study visit. During that initial study visit the patient will be randomized to one of the two treatment arms and the injection will be performed.

## Randomization Technique

Patients who meet the eligibility criteria will be assigned to steroid or PRP treatment using randomly assigned permuted blocks of 5, created with the random number generator function within STATA, to maintain equal group sizes.

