## Patient and Investigator Blinding

In order to keep the subject blinded towards the type of procedure all patients will have a blood draw. Study investigators and personnel, with the exception of [name] and [name], will be blinded. [name] will use the randomization code above and allocate consecutive patients to the intervention. When patients present for treatment, she will prepare the appropriate syringe (PRP or corticosteroid) and then place an opaque sleeve over it so as to conceal which intervention is being given. Each syringe will be marked with the patient's name, ID number, and will be labeled 'Investigational Use Only", and the intervention assigned to this patient will be recorded by [name]. This will ensure blinding of the patient, the treating physician ([name]), and the investigators.

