#### **Data Analysis:**

The study sample size is based upon power calculations for change in pain score data from a previous study by our group in patients with FAI. To detect a difference in the change in pain between the first and last visit of 1.7 units, on a 7-point pain scale, using a power of 80% and  $\alpha$ =0.05, requires at total N of 32, or 16 per group. To account for 20% of patients who might withdraw, we will recruit 8 additional subjects for a total of 40 patients. We will use a mixed-effects linear regression model to look at the changes in individual parameters at multiple time points over the course of the study, as well as the associations between changes of multiple parameters. Independent variables in the model are treatment assignment and time, dependent

variables are outcomes scores, biomarkers and Kellgren-Lawrence scores. First, we will perform univariate and univariable models to explore the relative importance of each predictor variable followed by a stepwise procedure in which we will include all significant variables in multivariable model followed by dropping the highest non-significant variable (significance will be set at p=0.10) until only significant variables remain. This will be repeated for each dependent variable. The robustness will be tested by performing model fitting and examining residual plots.

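### Permuted blocks of 5 cannot split equally between two arms, so the scheme does not reliably give the stated 20 per arm

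*Combined protocol and SAP*

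**What the plan says.** The Randomization Technique section allocates eligible patients to steroid or PRP by "randomly assigned permuted blocks of 5, created with the random number generator function within STATA, to maintain equal group sizes". Patient Selection confirms that there are two groups: "the patient will be randomized to one of the two treatment arms".

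The enrolment figures at the end of the Exclusion Criteria section read "N = 40 (n = 20 per arm". Data Analysis gives their origin. The power calculation "requires at total N of 32, or 16 per group", and the plan continues: "To account for 20% of patients who might withdraw, we will recruit 8 additional subjects for a total of 40 patients".

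Patient and Investigator Blinding adds only that an unblinded staff member "will use the randomization code above and allocate consecutive patients to the intervention". The one sentence in Randomization Technique is therefore the whole specification of the scheme. The document does not give a ratio within blocks, pair or alternate blocks in opposite directions, or vary the block size.

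**The concern.** A permuted block keeps two arms equal only if its size is even. With five places, one arm must receive more patients than the other in every complete block. The method is thus given a purpose that no single block can achieve, and whether the arms come out equal over the trial depends on a rule the plan does not state.

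What is at stake is mainly the accuracy of the randomisation description. The sentence does not settle which scheme generates the list, and the plain reading lacks the property claimed. Someone who later sees 22:18 under a plan promising equal groups could not tell whether the list had been followed. The size of the imbalance and its cost in power need checking before deciding how much weight the point deserves.

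This is not a point about concealment. The plan leaves the code with an unblinded allocator and blinds patients, the injecting physician and the investigators.

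**Working it through.** **Inputs from the document.** Block size 5 and two arms (Randomization Technique, Patient Selection); 40 patients, 20 per arm (end of Exclusion Criteria); 16 per group before withdrawals, 20% withdrawal, 80% power, α = 0.05 and a difference of 1.7 units (Data Analysis).

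**Assumptions.** (a) Each block is as balanced as five allows, 3:2 or 2:3. A 4:1 or 5:0 block would be further from equality. (b) The direction of each block is drawn independently with probability 1/2. (c) For power, a two-sided two-sample t-test. The document gives neither the SD nor the sidedness.

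**The plan's own figure.** 32 / (1 − 0.20) = 40, and 40 / 2 = 20 per arm. The total is reproduced.

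**Distribution of group sizes.** 40 / 5 = 8 complete blocks. Let K be the number of blocks that favour the steroid arm, so K ~ Binomial(8, 1/2). The steroid arm has 3K + 2(8 − K) = 16 + K patients, the PRP arm has 24 − K, and the difference is 2K − 8.

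| Split (either direction) | Probability |
|---|---|
| 20:20 | 70/256 = 27.3% |
| 21:19 | 112/256 = 43.8% |
| 22:18 | 56/256 = 21.9% |
| 23:17 | 16/256 = 6.3% |
| 24:16 | 2/256 = 0.8% |

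- Difference of 4 or more: (56 + 16 + 2)/256 = 74/256 = 28.9%.
- Mean absolute difference: 8 × 70/256 = 2.19 patients.

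**Dependence on assumption (b).** If exactly four blocks go each way, the result is always 20:20. If every block goes the same way, it is always 24:16. The chance of 20:20 therefore runs from 0% to 100%, depending on a rule the plan does not give.

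**Comparison with simple randomisation.** For Binomial(40, 1/2), 20:20 occurs in 12.5% of lists, a difference of 4 or more in 63.6%, and the mean difference is 5.0 patients. Blocks of 5 do limit imbalance; they do not secure equality.

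**Power.** Solving for 80% power at 16 per group gives a standardised difference of 1.024, that is an SD of 1.7 / 1.024 = 1.66. With 20% withdrawal in each arm, 24:16 becomes 19.2:12.8, or about 19:13.

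| Patients analysed | Split | Power |
|---|---|---|
| 32 | 16:16 | 80.0% |
| 32 | 17:15 | 79.8% |
| 32 | 18:14 | 79.4% |
| 32 | 19:13 | 78.6% |
| 40 | 20:20 | 88.4% |
| 40 | 22:18 | 88.1% |
| 40 | 24:16 | 87.1% |

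The greatest loss is 80.0 − 78.6 = 1.4 points with 32 completers and 88.4 − 87.1 = 1.3 points with 40 patients. The result is not sensitive to the SD. With all 40 patients, 20:20 against 24:16 gives 90.35% against 89.17% at SD 1.606 (a loss of 1.2 points) and 86.27% against 84.88% at SD 1.716 (a loss of 1.4 points).

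**The case against.** The strongest reply is that nothing of consequence follows. Under random directions, 27.3% + 43.8% = 71.1% of lists end at 20:20 or 21:19. The worst split costs little more than one point of power, the planned mixed model does not need equal arms, and the 20% withdrawal allowed for could unbalance the completers by as much. This stands and limits the weight of the point, but it does not make the sentence correct.

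A second reply is that the phrase about group sizes states a purpose and not a guarantee, and that 20 per arm is a planning number. Read as approximate balance, the method does work better than simple randomisation. That is fair as far as it goes, but the text says equal and an even block size would have delivered it.

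A third is that the number may be loose wording for 5 per arm (four blocks of 10) or for five blocks (of 8). Either would give exactly 20:20, and the fault would then lie only in the text. The document supports neither reading over the literal one, so the wording needs correcting in any case.

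Finally, the 27.3% rests on an unstated assumption. That is true, and the range is 0% to 100%. The conclusion does not need the figure: a complete block of 5 is unequal whatever rule sets its direction.

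**Conclusion.** The concern holds. As written, the allocation method does not have the property claimed for it, and nothing elsewhere in the document supplies that property. This rests only on five being odd and there being two arms.

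The chance of missing 20:20, 72.7% of lists, rests on independent random block directions. The power loss of at most about 1.4 points at the fitted SD of 1.66 rests on a two-sided t-test and on an SD back-solved from the plan's own sample size. The imbalance does not bias the treatment comparison and does not threaten the sample size. This is a certain but low-impact inconsistency in the randomisation specification, and it should be corrected because correction costs almost nothing.

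**What to change.** **If no list is in use.** Replace the block size with even blocks allocated 1:1 that sum to 40. For exact balance, any fixed even size that divides 40 is enough, such as ten blocks of 4, or four blocks of 10 if 5 per arm was meant. Mixed sizes in random order, known only to the unblinded allocator, are preferable because they also make the next assignment harder to predict; four blocks of 4 and four of 6 give 16 + 24 = 40. Each option yields exactly 20:20 at 40 patients. If recruitment stops early, the arms differ by at most 3 with blocks of 4 and 6, and by at most 5 with blocks of 10. The cost is a new list and one changed sentence.

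**If a list is already in use.** The document gives only "Proposed Study Start Date: 7/1/16", so this cannot be told from the text. Do not regenerate the list. Correct the sentence to state the block size, the ratio within blocks and any counterbalancing actually used, and remove the claim of equal group sizes if it does not hold. The cost is a one-sentence correction.

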## Blood Draws and Serum Preparation

Serum used for biomarkers analysis will be prepared from 4-5mL of blood drawn from an antecubital vein using standard clinical techniques. Serum will be aliquoted and stored in a deidentified fashion at -80°C until analyzed. CBC with Diff with also be done. This is being done one time to help evaluate patient's overall health.

## PRP Preparation

To maintain blinding, all patients will have approximately 125 mL of blood drawn from an antecubital vein. For those individuals who are in the PRP treatment group, PRP will be prepared by [name] who is trained in preparing PRP and who is unblinded to the treatment assignment. PRP will be prepared using a commercially available processing unit (Arthrex Angel system; Naples, FL). The Arthrex Angel unit is a FDA cleared system (510k)

number BK110046), and the PRP will be prepared using the manufacturers guidelines. Patients will remain in the treatment room while the PRP is being prepared. Once the blood is drawn from the patient, PRP is prepared using density gradient centrifugation with the processing unit mentioned above. Centrifugation takes approximately 20 minutes. Of the PRP that was collected small sample will be sent to the lab for CBC and diff analysis.

## Sterile Technique

For ultrasound guided procedures, a sterile probe cover will be used in addition to routine sterile techniques using Chloroprep cleansing solution and sterile drapes.

## Hip Intra-articular Corticosteroid

A 22-gauge spinal needle will be advanced from distal to proximal under ultrasound guidance towards the head-neck junction of the hip joint. Approximately 10 ml of 1% Lidocaine will be used for anesthesia of the skin and subcutaneous tissue. Once the hip joint has been reached, the injectate will consist of 4 ml of 10 mg/ml Kenalog for a total dose of 40 mg.

## Hip Intra-articular PRP

The hematocrit will be set at 2% to obtain a final product that is approximately 6-8 times higher than baseline in terms of platelet concentration. This approach will also produce a leukocyte-reduced preparation. Final product will be approximately 6-8 ml of platelet rich plasma.

A 22-gauge spinal needle will be advanced from distal to proximal under ultrasound guidance towards the head-neck junction of the hip joint. Approximately 10 ml of 1% Lidocaine will be used for anesthesia of the skin and subcutaneous tissue. Once the hip joint has been reached, the injectate will consist of the final PRP product (approximately 6-8 ml).

## Patient and Investigator Blinding

In order to keep the subject blinded towards the type of procedure all patients will have a blood draw. Study investigators and personnel, with the exception of [name] and [name], will be blinded. [name] will use the randomization code above and allocate consecutive patients to the intervention. When patients present for treatment, she will prepare the appropriate syringe (PRP or corticosteroid) and then place an opaque sleeve over it so as to conceal which intervention is being given. Each syringe will be marked with the patient's name, ID number, and will be labeled 'Investigational Use Only", and the intervention assigned to this patient will be recorded by [name]. This will ensure blinding of the patient, the treating physician ([name]), and the investigators.

## Post-Procedure Care:

Patients will remain in the clinic 30 minutes after injection to monitor for any adverse reactions.

All study patients will be advised to take Acetaminophen for up to 7 days post procedure, 650 mg every 6 hours as needed. Patients will also be provided with a standard FAI rehabilitation program^27.

Patients will be called 3-5 days after the procedure to collect information on any potential adverse events or reactions to the injection

## Follow-up Visits:

Subjects will return to the clinic at 6 weeks, 3 months, 6 months and 12 months. At each visit, the following will be performed:

- Physical exam;
- 7 point visual analog pain scale;
- the WOMAC, the HOOS, and the PROMIS Global Health scale;
- Hip Radiographs including standing AP pelvis, lateral Dunn views, and false profile view (initial encounter and at 12 months only);
- serum biomarkers (IFN-g, IL-6, MCP-1, MIP-1b, IL-1b, TNF-alpha, highly sensitive CRP, COMP) at all time points; and
- any adverse events, regardless of severity

# **Billing:**

Neither patients nor their insurance companies will be billed for the costs of injection of steroid or PRP, blood draws or radiographs used in the study.

#### Risks:

Standard risks involved with intra-articular hip injection including bleeding, infection, nerve damage, increased pain, reaction to anesthetic.

For Kenalog, complications are infrequent, though some mild local complications may occur, as listed in the FDA approved label dated June 2011. Some of these are atrophy of the skin at the injection site, facial flush, and post-injection flare (soreness and inflammation following the injection). Systemic side effects such as infection, increased blood glucose, hypercortisolism, and others are rarely seen. There is a rare risk of anaphylaxis, including death

#### **Confidentiality:**

Standard clinical protocol regarding patient confidentiality. All data will be maintained by the primary investigator in a locked office and password-protected computer.

#### **Data Collection:**

Data collection will be collected and entered by orthopedic surgery research team member assigned to the study and stored into a REDCap database via Ipad. This includes clinical data, radiographic data and analysis of serum biomarkers.

Subjects' hip pain levels will be assessed via standardized orthopedic survey tools (7 point pain VAS, Western Ontario and McMaster Universities Arthritis Index (WOMAC), Hip Disability and Osteoarthritis Outcome Score (HOOS), Patient Reported Outcome Measurement Information System (PROMIS) Global Health Scale) at baseline, 6 weeks, 3 month, 6 months, and 12 months.

Hip radiographs will be performed at baseline and at 12 months, and graded Stage 1-4 via Kellgren-Lawrence classification in a blinded fashion by [name] as described.

Biomarkers analysis will be performed in [name] lab as described. Serum will be aliquoted and stored at -80°C in a de-identified fashion in secured freezers in [name] lab.

Samples will be analyzed in duplicate at each time point, and interassay coefficients of variation will be calculated. For hsCRP (Calbiotech) and COMP (R&D Systems), ELISAs will be performed following manufacturer's instructions. For IFN-g, IL-6, MCP-1, MIP-1b, IL-1b and TNF-alpha, a multiplex Luminex-based assay (Millipore) will be performed following manufacturer's instructions.

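### The Kellgren-Lawrence reading scale starts at 1 while the numeric entry limit has no lower bound, so a first step of radiographic change may go unrecorded if hips without osteoarthritis are enrolled

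*Combined protocol and SAP*

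**What the plan says.** Data Collection states that hip radiographs from baseline and 12 months are "graded Stage 1-4 via Kellgren-Lawrence classification", with the reader blinded. It gives no other grading range and does not say how a hip with no radiographic osteoarthritis is coded.

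The Inclusion Criteria contain "Mild to moderate osteoarthritis (Kellgren-Lawrence grade" followed by ≤ 2. The number has no lower bound, while the words in front of it name a disease state. The Exclusion Criteria remove the upper end, "High grade osteoarthritis (Kellgren-Lawrence" followed by ≥ 3, and also hips with a minimum joint space under 2 mm. Nothing excludes a hip because it has no osteoarthritis. The age limits are given as "Minimum Age: 18 Maximum Age: 45".

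The grade is used as an outcome in three places:

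- Specific Aims, Hypothesis 2(i), predicts "a diminished change in Kellgren-Lawrence radiographic scores" with PRP compared with corticosteroid.
- Secondary Outcome(s) lists "Change in Kellgren-Lawrence classification scores calculated from anterior-posterior (AP) pelvis radiographs between pre-treatment and 1 year post-treatment", and the plan for measuring the outcomes repeats it.
- Data Analysis makes it a dependent variable of the mixed-effects linear model: "variables are outcomes scores, biomarkers and Kellgren-Lawrence scores".

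**The concern.** A change score can show only the steps that its scale can code. If some hips enter without radiographic osteoarthritis and the lowest available code is 1, those hips share a code with true grade 1 hips. Their first step of change then disappears.

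The protocol gives some reason to expect such hips among candidates. It defines FAI by cam, pincer or combined morphology on the radiograph, not by osteoarthritis. The Background treats FAI as what sets hip osteoarthritis in motion, so impingement comes first. Participants are 45 or younger.

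At stake is the sensitivity of the radiographic half of Aim 2. The hypothesis compares change between arms, so steps lost in both arms shrink the contrast being tested.

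**Working it through.** The plan states no sample size, power or expected progression rate for this outcome, so there is no figure to reproduce. The check has two parts.

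**1. What a 1-4 scale records**

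Inputs: the 1-4 range (Data Collection) and the entry limit of 2 (Inclusion Criteria). Assumption: a hip with no radiographic osteoarthritis is labelled 0 here and would be recorded as 1. The documents name no grade 0.

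Recorded grade = max(true grade, 1). Recorded change = recorded grade at 12 months minus recorded grade at baseline.

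| True baseline | True 12 months | True change | Recorded change |
|---|---|---|---|
| 0 | 1 | 1 | 0 |
| 0 | 2 | 2 | 1 |
| 0 | 3 | 3 | 2 |
| 1 | 2 | 1 | 1 |
| 1 | 3 | 2 | 2 |
| 2 | 3 | 1 | 1 |
| 2 | 4 | 2 | 2 |

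Every hip that starts at 0 and progresses loses one step. Changes from grades 1 and 2 are recorded correctly.

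**2. How much could be lost**

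Let f be the share of patients who enter without osteoarthritis and q the probability of a one-step progression in 12 months, assumed equal at every grade. With n patients in an arm:

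- true progressions = n × q
- recorded progressions = n × q × (1 - f)

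If f is the same in both arms, the expected difference between arms is multiplied by the same (1 - f).

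For illustration, take n = 16 per arm (the evaluable number in Data Analysis, which was set for pain) and q = 0.10 (an assumption). True progressions per arm are 16 × 0.10 = 1.6. Recorded progressions per arm are:

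| f (assumed) | Calculation | Recorded | Loss |
|---|---|---|---|
| 0 | 1.6 × 1.00 | 1.6 | 0% |
| 0.10 | 1.6 × 0.90 | 1.44 | 10% |
| 0.25 | 1.6 × 0.75 | 1.2 | 25% |
| 0.50 | 1.6 × 0.50 | 0.8 | 50% |
| 0.75 | 1.6 × 0.25 | 0.4 | 75% |

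The percentage loss does not depend on q. With q = 0.05, 0.8 true progressions per arm become 0.2 at f = 0.75, again a 75% loss. The documents give neither f nor q.

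**The case against.** The strongest reply is that the entry criterion should be read whole. The number stands in parentheses after a condition the patient is to have. On that reading osteoarthritis is required, entry covers grades 1 and 2, f = 0, and the 1-4 scale has no gap. The text permits this reading.

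It does not remove the need for an edit. If the words govern, hips without osteoarthritis have to be screened out, yet no lower limit is written. The only grading range in the protocol also cannot separate none from grade 1, so the recorded grade could not show that the criterion was met.

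A reader might infer more than the documents support:

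- **That patients without osteoarthritis must be coded 1 and that their first step cannot be recorded.** Both depend on such patients being enrolled and coded that way. The protocol says neither. It refers to a cited source for the grading method, and that source was not available here.
- **That a definite number of progressions will be missed.** No progression rate or share without osteoarthritis appears in the documents, and an honest range for the loss starts at zero.
- **That the earliest step is the most likely change in this cohort.** No progression rates by grade are given.
- **That the arms are biased against each other.** Allocation is randomised and grading is blinded, so a floor would apply to both arms alike. The effect is lost sensitivity.

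It is also fair to say that so few progressions may occur that the comparison is uninformative on either scale. The illustrative counts above, under 2 per arm, agree with that. This limits the importance of the point but is no reason to keep a scale with a possible gap.

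**Conclusion.** The point holds in conditional form. The lower end of the grading scale and the lower limit of eligibility are not aligned: Data Collection has no code for a hip without radiographic osteoarthritis, and the Inclusion Criteria can be read as admitting such hips or as excluding them.

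If they are enrolled and recorded as 1, each of them that progresses loses one recorded step. Under equal one-step progression at every grade, recorded progressions fall by the factor (1 - f), from no loss at f = 0 to a 75% loss at f = 0.75. Where the trial would fall in that range is unknown.

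The effect is confined to Hypothesis 2(i), a secondary outcome. The primary VAS outcome and the sample size, which was set on pain, are untouched. Severity is minor. The change is worth making because it costs almost nothing, loses nothing if no such hip enrols, and recovers the change if any do.

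**What to change.** 1. In Data Collection, grade the films on a range that includes a code for no radiographic osteoarthritis (0-4). The reader, films and visits stay the same.
2. In the Inclusion Criteria, reconcile the wording with the numeric limit so that the lowest eligible grade is explicit. Whether hips without radiographic osteoarthritis are eligible is the sponsor's decision. It defines the study population and should not be settled as a by-product of correcting the scale.

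The first change is one edit to a stated range. The second is a wording edit once the sponsor has said which population is meant. If films have already been graded with only 1-4 stored, any lost first steps can be recovered only by re-reading the films recorded as 1 at baseline under the same blinding, together with their 12-month films.
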